COVER PAGE FOR PROTOCOL AND STATISTICAL ANALYSIS PLAN

Official Study Title: The Effects of a Music Intervention on Stress, Anxiety and Academic Performance on Nursing Students

NCT number: NCT05590910

IRB Approval Date: 05.23.2022

Unique Protocol ID: HSC20210672H

Protocol Template Form

Item 1 UTHSCSA Tracking Number	HSC20210672H: The Effects of a Music Intervention on Stress, Anxiety and Academic Performance on Nursing Students
---------------------------------------	--

Item 2 Abstract / Project Summary	Provide a succinct and accurate description of the proposed research. State the purpose/aims. Describe concisely the research design and methods for achieving the stated goals. This section should be understandable to all members of the IRB, scientific and non-scientific. DO NOT EXCEED THE SPACE PROVIDED.
--	--

Purpose/Objectives: The purpose of this study is to assess whether a music intervention, compared with no music intervention, influences stress and anxiety levels and academic performance of undergraduate nursing students.

Research Design/Plan: A randomized controlled approach will explore the effects music has on stress and anxiety levels and academic performance among undergraduate nursing students.

Methods: Students will be divided and randomized into two recording groups: 1.) Music Intervention Group, 2.) Non-Music Control Group. The music intervention group will receive a 15-minute music intervention and variables such as heart rate, blood pressure, anxiety, and academic performance will be measured. The non-music control group will not receive the intervention; however, the same variables will be measured.

Clinical Relevance: Music has been shown to beneficially affect stress-related physiological, as well as cognitive, and emotional processes. The proposed study has the potential to highlight the acceptance of music used as a strategy for impacting stress and anxiety experienced by nursing students during their undergraduate studies. Evidence of any effect music has on stress and anxiety levels among undergraduate studies can determine existence by the measurement of vital signs, STAI responses, and skills performance. This type of study can be beneficial to further research and can be implemented by nurse educators, healthcare institutions, and wellness clinics.

Item 3 Background	
Describe past experimental and/or clinical findings leading to the formulation of your study. For research involving unapproved drugs, describe animal and human studies. For research that involves approved drugs or devices, describe the FDA approved	Nursing students experience higher levels of stress than students in any other health science academic programs (Kinchen & Loerzel, 2019). Since most nursing students are not able to avoid these stressors, students must be able to cope with them. If students are not able to manage their stress, it can affect their performance, health, attitude, and role satisfaction as a nurse (Rafati et al., 2017). The levels of stress may vary during students' educational training, depending on their ability to adopt various strategies or coping with stress, and other factors. Even though numerous studies have been published regarding stress and anxiety among nursing students, few studies are found addressing the benefits of music utilized as an intervention to decrease emotional stress.

uses of this drug/device in relation to your protocol.
	

Item 4 Purpose and rationale Insert purpose, objectives and research questions/hypotheses here. If you cut and paste from another document, make sure the excerpted material answers the question
	
Music is an immensely powerful emotional tool that can be used as a coping mechanism for stress, but there is truly little existing research about its use by students. This study aims to explore the effects of music intervention on the stress and anxiety levels among nursing students in their first semester of undergraduate studies. Increased awareness of their own strategies used, as well as the willingness to use holistic methods such as music, can offer a non-pharmacological and inexpensive intervention to many institutions.
 
Research Questions:
 
 1. Is there a relationship between listening to music and stress, anxiety, and academic performance among new undergraduate nursing students? 2. Does listening to music help in decreasing anxiety among new undergraduate nursing students who are anticipating a skills assessment? 3. Does listening to music help in decreasing stress among new undergraduate nursing students who are anticipating a skills assessment? 4. Does listening to music help to improve academic performance among new undergraduate nursing students?


Item 5 Study Population(s) Being Recruited
	
In your recruitment plan, how many different populations of prospective subjects do you plan to target? Provide number: 1
	

e.g., a population can be individuals with type 2 diabetes controlled with diet and/or a population of healthy controls. Or a population can be individuals attending an education program, etc.
 
List each different population on a separate row and provide a short descriptive label: (e.g., normal-healthy, diabetics, parents, children, etc.)
	
Identify the criteria for inclusion:
	
Identify the criteria for exclusion:

To add rows use copy & paste
 
Nursing Students
	
18 years and older Enrolled at UTHSCSA- School of Nursing Enrolled in a Foundations of Nursing Clinical course First semester undergraduate nursing student
	
Younger than 18 years old 2nd , 3rd ,4th semester undergraduate nursing student

Insert response here	Insert response here	Insert response here
----------------------	----------------------	----------------------

Item 6

Research Plan / Description of the Research Methods *a. Provide a comprehensive narrative describing the research methods. Provide the plan for data analysis (include as applicable the sample size calculation).*

Step-by-Step Methods:

A randomized controlled approach will explore the effects music has on stress and anxiety levels and academic performance among undergraduate nursing students. The study will be conducted with nursing students in the first semester of the undergraduate BSN program at UT Health Science Center at San Antonio. The study will consist of Phase 1 (pilot) and Phase 2 (larger dissertation study). Phase 1 will be the pilot study conducted in Spring 2022. The total population of the cohort typically consists of \approx 108 students. Approximately half-way through the semester, the students are required to sign-up for a skills competency recording. The students select the best date and time for their schedule. Students sign-up electronically into a group consisting of up to 10 students. Typically, there are 30 min time slots available for sign-up. For Phase 1, the pilot study will use a cluster randomization procedure to randomly assign two of the sign-up groups. The two groups will be 1) the music intervention group (n=up to 10 participants), and 2.) the non-music control group (n= up to 10 participants). An online randomizer will be used to create the groups. Students assigned to these groups will be allowed to remove themselves. The academic performance of these students will be recorded for the study.

Phase 2 of the study will be informed from the findings of Phase 1, the pilot study. It is anticipated there will be no intended changes in the methodology or randomization procedures from Phase 1 to Phase 2. The only difference would be in Phase 2 the total population in the Summer 2022 cohort (\approx 108) will be randomized into approximately 6 slots per half hour. Any changes to be made for Phase 2 will be immediately communicated to the IRB for approval prior to implementation.

The following procedures will be used for Phase 1 and Phase 2:

The study will be conducted at the UT Health Science Center - San Antonio's Center for Simulation Innovation (CSI). Two classrooms will be reserved in the CSI area at the School of Nursing. Students will be divided into the recording time slots consisting of no more than 10 students at a time. The students receiving the music intervention will be assigned an iPad (only used to sync smartwatch), a hard copy of State Trait Anxiety Inventory (STAI) survey forms Y-1 and Y-2, a demographic data form, pencil, and smart watch. Students will be advised to sit quietly, with desks spread out, in the reserved room. The participants will be asked to complete the STAI survey forms prior to music listening. Students will be advised to wear the watch, and watches will be previously logged in and synced by researcher to measure heart rate and blood pressure. Vital sign sheet will be completed by researcher using the data from the iPad. Fifteen minutes of classical music will be played overhead in the classroom. The students will be instructed not to use other electronic devices such as ear buds or phones during this time. The STAI survey Y-1 will be completed again post-intervention, and heart rate and blood pressure re-assessed. Students will then proceed to perform the skills competency assessment. Vitals and STAI survey Y-1 will then be reassessed post-skills competency and academic performance (pass/fail) will be measured.

The students who will not be receiving the music intervention (control group) will be seated in a second reserved classroom and will be repeating the same process as the music intervention group except without music, instead they will be sitting quietly for 15 minutes waiting to record their skills competency. The students will also be instructed not to use other electronic devices such as ear buds or phones during this time. For any students who have been randomly assigned to either group, and refuse to be in the study, they

will be allowed to leave. Only the academic performance will be measured on these students that refuse to be assigned to a group.

Data Analysis Plan:

A priori power analysis was conducted using G*Power 3.1.9 to determine the minimum sample size required to find statistical significance using a 3 (group) x 4 (time) repeated measures analysis of variance (i.e., a mixed-model ANOVA). With a desired level of power set at .80, an alpha (α) level at .05, and a moderate effect size of .25 (f), it was determined that a minimum of 30 total participants would be required to ensure adequate power (Cohen, 1988).

Mean heart rate, mean blood pressure, mean scores on STAI, and academic performance score (Pass/Fail) will be calculated for all groups. Demographic data will be analyzed in terms of frequencies and comparisons between groups. For RQ1: Pearson's correlation will examine the relationship between the music intervention on stress, anxiety, and academic performance. For RQ2: To measure anxiety, STAI mean scores will be analyzed. For RQ3: To measure stress levels, the mean heart rate and mean blood pressure will be analyzed. For RQ4: To assess academic performance, Pass/fail scores will be looked at. MANOVA will be considered for data analysis since there is one independent variable (music intervention) and multiple dependent variables. If any variables are not correlated, running a repeated-measures ANOVA to detect any overall differences between any related means would be considered. A paired samples t-tests could also be used for pre-and post-comparisons of vital signs. Using a Chi-Square test can also be beneficial in determining any differences in demographics and anxiety and/or stress. Alpha will be set at 0.05 for the study.

Item 7 Risks Section:

Complete the following table to describe the risks of all **research procedures** listed in Step 2, Institutional Form (items 28-34). *Do not list risks of Routine care procedures here.*

N/A, Risks are described in the informed consent document – do not complete this table.

Research procedures	Risks

example:
 
 • History and physical • Questionnaire • Laboratory tests 	
List the reasonably expected risks under the following categories as appropriate:

Add or delete rows as needed	
Vitals Signs obtained via SmartWatch	
Serious and likely;
 
 ○ None 
Serious and less likely;
 
 ○ None
Heart Rate Blood Pressure	
Demographic data form, paper and pencil	
Serious and likely;
 
 ○ None
STAI Survey: paper and pencil survey	
Serious and likely;
 
 ○ None
Academic Performance	
Serious and likely;
 
 ○ Pass/Fail

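### Phase 1 has one sign-up group and one room per arm, so a student-level test of music cannot be interpreted; Phase 2 leaves the randomised unit undefined

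*Combined protocol and SAP*

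**What the plan says.** **Phase 1 design (Item 6, Step-by-Step Methods).** Students form sign-up groups of up to 10 by choosing their own time: "The students select the best date and time for their schedule". Then: "For Phase 1, the pilot study will use a cluster randomization procedure to randomly assign two of the sign-up groups". The allocation is one group per arm: "The two groups will be 1) the music intervention group (n=up to 10 participants), and 2.) the non-music control group", the latter also of up to 10. The next sentence adds: "An online randomizer will be used to create the groups". The procedures play the music over the classroom's speakers to everyone present and seat the control students in a different classroom.

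**Phase 2 design (same section).** "Phase 2 of the study will be informed from the findings of Phase 1, the pilot study". On allocation: "It is anticipated there will be no intended changes in the methodology or randomization procedures from Phase 1 to Phase 2". Yet the one stated difference is that the whole cohort of about 108 "will be randomized into approximately 6 slots per half hour".

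**Analysis (Data Analysis Plan).** One plan serves both phases. Pearson's correlation is the committed analysis relating music to stress, anxiety and academic performance (RQ1), and alpha is 0.05 for the study. MANOVA and repeated-measures ANOVA are mentioned only as things to be considered. No group, session, slot or room term appears anywhere, and no sentence confines Phase 1 to feasibility or description.

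**The concern.** In Phase 1 each arm is a single self-selected group in a single room. Anything shared by that group (time of day, who chose that slot, the room, the session itself) shifts all of its students together and looks exactly like an effect of music. A student-level p-value is valid only if no such shared effect exists, and with one group per arm the data cannot check this. The result matters beyond the pilot because Phase 1 findings are meant to inform Phase 2.

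In Phase 2 the stake depends on what is randomised. If whole sessions are allocated, ignoring session makes student-level tests reject too often. If students are allocated within slots and share only a slot effect, there is no inflation. If each classroom always hosts the same arm, a lasting room difference cannot be told apart from music by any analysis. The plan does not say which of these applies.

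**Working it through.** **The plan's own figure.** The stated minimum is 30, for 3 groups × 4 times, f = 0.25, alpha 0.05 and power 0.80. Assume a correlation of 0.5 between repeated measures and sphericity (neither is stated). For the within-between interaction, the noncentrality is 0.25² × 30 × 4 / (1 − 0.5) = 15, with df 2 × 3 = 6 and 27 × 3 = 81. Power is 0.809, so 30 reproduces. The calculation treats students as independent. Phase 1 has at most 2 × 10 = 20 students, below 30, so the calculation cannot describe Phase 1.

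**Level of the planned correlation.** With two groups, a group-level correlation can only be +1, −1 or undefined. The RQ1 correlation must therefore be run on students. Between-cluster degrees of freedom are 2 groups − 2 arms = 0, so no cluster-adjusted alternative exists.

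**Phase 1, continuous outcome at a single time (exact).** Testing a correlation with a two-level arm is the two-sample t-test on 18 df. With m = 10 per group, the statistic is inflated by c = √[(1 + 9·ICC)/(1 − ICC)], and the true type I error is 2·P(t₁₈ > 2.101/c).

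| Assumed ICC | c | 2.101/c | Type I error |
|---|---|---|---|
| 0.02 | √(1.18/0.98) = 1.097 | 1.915 | 7.2% |
| 0.05 | √(1.45/0.95) = 1.235 | 1.701 | 10.6% |
| 0.10 | √(1.90/0.90) = 1.453 | 1.446 | 16.5% |

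**Phase 1, pass/fail (simulated, beta-binomial groups, 100,000 null trials per cell; pass rates assumed).**

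| Pass rate | No clustering | ICC 0.02 | ICC 0.05 | ICC 0.10 |
|---|---|---|---|---|
| 70% | 3.6% | 5.7% | 8.7% | 14.0% |
| 80% | 2.9% | 4.5% | 7.0% | 11.3% |
| 90% | 0.9% | 1.8% | 3.3% | 6.0% |

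Discreteness keeps the unclustered test below 5%, which hides part of the inflation.

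**What Phase 1 loses without the test.** Significance needs |r| > 2.101/√(18 + 2.101²) = 0.444. Reading f = 0.25 as d = 0.5 for two groups, power with 10 per arm is 18.5%.

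**Phase 2, conditional.** The number of sessions is not stated; the layouts below are assumed (normal outcome, simulated). The first case is whole sessions randomised with a student-level test:

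| Layout per arm | ICC 0.02 | ICC 0.05 | ICC 0.10 |
|---|---|---|---|
| 5 sessions of 10 | 7.1% | 10.3% | 15.6% |
| 9 sessions of 6 | 6.1% | 7.9% | 11.1% |
| 18 sessions of 3 | 5.4% | 6.0% | 7.3% |

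A t-test on session means holds at 4.9–5.1% if there is no lasting room effect.

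The other cases:
- **Students randomised within 18 slots, 3 per room, shared slot effect only.** At ICC 0.02 / 0.05 / 0.10, the student-level test runs at 4.8 / 4.5 / 3.9%, and paired room means within slot at 5.0 / 5.0 / 4.9%.
- **Each room fixed to one arm, room effect 2 / 5 / 10% of variance.** The session-mean test rejects in about 11–17 / 20–30 / 32–45% of null trials across layouts (session ICC 0 or 0.05). The paired slot test rejects in 17.3 / 30.5 / 45.0% (slot ICC 0.05).
- **Rooms alternated between arms, with a room term.** 4.8–5.2% for session means and 5.0–5.1% for paired slots.

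**The case against.** The best defence has four parts.

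- **Phase 1 is labelled a pilot and is smaller than the powered minimum**, so the inferential plan may have been written for Phase 2. That is plausible, but the Data Analysis Plan is not divided by phase and the label restricts no analysis.
- **The correlation could be descriptive**, since no p-value is mentioned beside it and alpha comes later. It is true that a test is not spelled out. A committed analysis together with a study-wide alpha is nevertheless most naturally read as a test at 0.05.
- **STAI and vital signs are taken before and after the intervention**, so in a change score a constant group or room effect cancels. This is correct and limits the continuous figures above to single-time comparisons. But no change score is named for RQ1, group-by-time variation would not cancel, and pass/fail has no baseline. For pass/fail, several cells do stay below 5%.
- **The online randomiser might randomise group membership.** That would remove prior differences between the groups, but one session and one room per arm would remain.

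Two further points also stand. Every ICC, room variance and Phase 2 layout is an assumption. And Phase 1 was scheduled for Spring 2022 while the cover page dates IRB approval 05.23.2022, so the Phase 1 design may no longer be changeable; its analysis and reporting are a matter of wording.

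**Conclusion.** The concern holds. For Phase 1 the plan is wrong as written: arm is completely confounded with sign-up group and room, and the committed student-level correlation cannot support a statement about music. That conclusion needs no ICC. Its size does: the nominal 5% becomes 7.2–16.5% for a continuous outcome at one time, over an assumed ICC of 0.02–0.10 with groups of 10, and 1.8–14.0% for pass/fail over assumed pass rates of 70–90%. This must be corrected, with high confidence, and that rating applies to Phase 1 only. MANOVA and repeated-measures ANOVA are optional in the plan and are not part of the finding.

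For Phase 2 the firm part is that the two statements about randomisation point to different units and that no session, slot or room term is named. Whether error rates are inflated depends on the unit chosen and on whether rooms stay fixed to arms.

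**What to change.** 1. **Phase 1.** State that arm comparisons are for description and feasibility only (means, SDs, completion), with no significance tests between arms. Cost: the Phase 1 arm p-values.
2. **Phase 2 unit.** State what is randomised and the planned number of sessions per arm, and record a slot ID and a room ID for each student.
3. **Phase 2 analysis.** If sessions are randomised, fit session as a random effect with small-sample degrees of freedom, or use a t-test on session means (session pass proportions for pass/fail). If students are randomised within slots, treat slot as a block and compare paired room means.
4. **Rooms.** Alternate the two classrooms between arms across sessions and add a room term. Otherwise, state that a lasting room effect cannot be separated from music.

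The outlay is plan wording, two recorded IDs, and either moving the music between rooms or one limitation sentence. Relative to student-level intervals, confidence intervals for session means widen by (t critical on sessions − 2 df ÷ t critical on students − 2 df) × √(1 + (m − 1)·ICC). At ICC 0.02–0.10 this is 5–12% (18 sessions of 3 per arm), 12–31% (9 of 6) or 26–60% (5 of 10). Adding a room term makes it about 5–12%, 13–33% or 32–68%. With slot as a block the widening is only about 1–6%.

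### RQ4 asks about academic performance in general, but rests on one pass/fail result from one skills check straight after one 15-minute session, with no expected pass rate and no sample size for it

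*Combined protocol and SAP*

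**What the plan says.** Item 4 lists four research questions. Questions 2 and 3 are limited to students who are about to take a skills assessment. Question 4 has no such limit: "Does listening to music help to improve academic performance among new undergraduate nursing students". Question 1 also names academic performance without restriction.

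Item 6 describes the exposure, "Fifteen minutes of classical music will be played overhead in the classroom", and what follows it, "Students will then proceed to perform the skills competency assessment". The assessment is a single mid-semester event: "Approximately half-way through the semester, the students are required to sign-up for a skills competency recording". The result is then recorded: "Vitals and STAI survey Y-1 will then be reassessed post-skills competency and academic performance (pass/fail) will be measured".

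The Data Analysis Plan in Item 6 says of this outcome only: "For RQ4: To assess academic performance, Pass/fail scores will be looked at". It names no test, effect size or expected pass rate for RQ4. The one sample-size statement, a minimum of 30 participants, is for a 3 (group) x 4 (time) repeated-measures ANOVA with f = 0.25 and power 0.80. The significance level is general: "Alpha will be set at 0.05 for the study".

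**The concern.** There are two separate problems.

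The first is scope. A single skills check taken straight after a short exposure can speak to performance on that check. It cannot speak to academic performance among new nursing students more widely. The plan contains no course grade, examination, later assessment, graded score or baseline. Without a baseline, improvement can only mean a difference between the two groups.

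The second is coarseness. A pass/fail result discards all variation on either side of the pass mark. If most students pass, few failures remain to be prevented, and even a worthwhile benefit may leave no visible difference.

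Together these make a null result on RQ4 easy to misread. It could be reported against an unrestricted question as music not helping academic performance, when the trial had looked only at who cleared one threshold shortly afterwards and had limited ability to see a difference.

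**Working it through.** **1. The plan's own figure.** Inputs from the Data Analysis Plan: 3 groups, 4 times, f = 0.25, alpha 0.05, power 0.80. Assumed, because not stated: correlation between repeated measures 0.5 and no sphericity correction. For the group-by-time interaction, the noncentrality is f² × N × m / (1 − rho).
- N = 30: 0.0625 × 30 × 4 / 0.5 = 15, with 6 and 81 degrees of freedom; power 0.809.
- N = 27: noncentrality 13.5, with 6 and 72 degrees of freedom; power 0.754.

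The stated 30 therefore reproduces. It concerns an outcome measured repeatedly on a continuous scale. Pass/fail is binary and measured once, so this figure says nothing about RQ4.

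**2. Inputs for pass/fail.**
- Arm size: the Phase 2 cohort of about 108, divided equally, gives 108 / 2 = 54 per arm. The equal split is assumed.
- Test: two-sided Fisher exact at 0.05. The plan names no test and no sidedness, so this too is assumed.
- Control pass rate: not in the documents. A range from 50% to 95% is shown.
- Students are treated as independent and nobody refuses.

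**3. Power if music halves the failure rate.** With control failure rate q, power is the sum, over all failure counts x (control) and y (music), of Bin(x; 54, q) × Bin(y; 54, q/2), counting only pairs with Fisher p < 0.05.

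| Control pass rate | Music pass rate | Power |
|---|---|---|
| 50% | 75% | 72% |
| 70% | 85% | 37% |
| 80% | 90% | 21% |
| 85% | 92.5% | 14% |
| 90% | 95% | 7% |
| 95% | 97.5% | 1.5% |

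No entry reaches the plan's own target of 80%.

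**4. Power if every music student passes.** With 0 failures of 54 on music, 5 control failures give p = 0.057 and 6 give p = 0.027, so at least 6 are needed. Power is then the probability of 6 or more control failures, P(Bin(54, q) ≥ 6).

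| Control pass rate | Power |
|---|---|
| 80% | 97% |
| 85% | 84% |
| 90% | 46% |
| 95% | 5% |

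**5. Smaller sizes.** At 15 per arm (the stated minimum of 30), with no music failures, at least 5 control failures are needed, a control pass rate of 10/15 = 67% or less. At 10 per arm (the pilot), again at least 5 are needed, a pass rate of 50% or less.

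**6. What a score could recover.** Suppose that pass/fail is a cut on a normally distributed score and that music shifts the mean enough to halve failures. The shift in standard deviations is z(1 − q/2) − z(1 − q). A two-sided t-test on the score, 54 per arm, compares with pass/fail as follows.

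| Control pass rate | Shift (SD) | Power, score | Power, pass/fail |
|---|---|---|---|
| 70% | 0.51 | 75% | 37% |
| 80% | 0.44 | 62% | 21% |
| 85% | 0.40 | 55% | 14% |
| 90% | 0.36 | 46% | 7% |
| 95% | 0.32 | 37% | 1.5% |

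Normality is an assumption. A real checklist score may be skewed, so the gain is indicative only.

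**The case against.** A reader might infer that this outcome sits near its ceiling and so cannot show improvement, whatever music does. The documents do not support that. They give no pass rate, pass mark, grading standard or rule on repeat attempts. The risk table in Item 7 lists pass/fail against academic performance under the serious and likely category; the entry is ambiguous, but it does not suggest near-universal passing. Step 4 shows that a very large effect would be detectable in the full cohort at a control pass rate of about 85% or lower. The ceiling is a condition, not a finding.

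The measure is also disclosed. The abstract names skills performance as part of the evidence, and Item 6 labels the outcome pass/fail in both the procedures and the analysis. A careful reader would know what was measured. This narrows the scope point to the wording of RQ4 and RQ1, but that wording still invites a broader answer than the data can give.

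Phase 2 is to be informed by the pilot, so a pass rate will be seen first. That is fair, and for the same reason little weight belongs on power at the pilot's size. But the plan anticipates no change in methods between phases and does not say that the pilot pass rate will be used to revisit this outcome.

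Finally, no checklist, item score or grading procedure is mentioned, so a graded outcome cannot be assumed to be available. That stands, and the second part of the fix is conditional on it.

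**Conclusion.** The point holds in two parts. Without any assumption, one pass/fail result on one skills competency directly after one 15-minute session cannot answer a question about academic performance in general, and the plan neither states an expected pass rate nor sizes the study for this outcome.

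Under the stated assumptions (54 per arm, independent students, two-sided Fisher test), power to detect a halving of failures falls from about 72% at a 50% control pass rate to 1.5% at 95%. Refusals, which Item 6 allows, would lower these figures. So would clustering: Phase 1 randomises sign-up groups, and no change of procedure is anticipated for Phase 2. A benefit is therefore hard to detect if most students pass, though a very large one could still appear at a control pass rate of about 85% or lower.

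The anxiety and stress questions are not affected. The change should be made, because it concerns one of the four research questions and an outcome named in the study title.

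**What to change.** 1. Reword RQ4, and the academic-performance part of RQ1, to performance on the skills competency taken immediately after 15 minutes of music. Limit the conclusion to that, so that a null result is not read as no effect on academic performance.
2. If the competency is graded with a checklist or numeric score, or the existing grader can tick steps without extra staff, record that score for participants and make it the RQ4 outcome, with pass/fail reported descriptively beside it. Students who decline would contribute no more than the pass/fail result that the plan already records for them.
3. If no such score can be had, keep pass/fail and report the difference between groups with a confidence interval, so that the uncertainty is visible.

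The cost is a narrower claim, revised wording, and one extra data field or some extra effort by the grader.

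### As written, Phase 2 plays music in one classroom and seats controls in a second with no rotation described, so room is confounded with arm

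*Combined protocol and SAP*

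**What the plan says.** All of this stands in Item 6, Step-by-Step Methods, unless another place is named.

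- **Rooms.** "Two classrooms will be reserved in the CSI area at the School of Nursing".
- **Music arm.** Students sit in the reserved room, and "Fifteen minutes of classical music will be played overhead in the classroom". In any one session a whole room is therefore one condition.
- **Control arm.** Students "will be seated in a second reserved classroom and will be repeating the same process as the music intervention group except without music". They wait quietly for 15 minutes.
- **Both phases.** "The following procedures will be used for Phase 1 and Phase 2". The protocol adds: "It is anticipated there will be no intended changes in the methodology or randomization procedures from Phase 1 to Phase 2". The one difference it names is that the whole Summer 2022 cohort of about 108 "will be randomized into approximately 6 slots per half hour".
- **Session size.** "Students will be divided into the recording time slots consisting of no more than 10 students at a time".
- **Staff and devices.** "Vital sign sheet will be completed by researcher using the data from the iPad". The watches are logged in and synced beforehand by the researcher. The number of researchers is not given, and neither a researcher nor a watch set is assigned to a room.
- **Measurements.** State anxiety (STAI Y-1), heart rate and blood pressure are taken before the 15 minutes, after them, and again after the skills assessment.
- **Analysis (Data Analysis Plan).** MANOVA, repeated-measures ANOVA and paired t-tests are mentioned as options. None has a room or session term.

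No section says that the classrooms are swapped, alternated or randomized between the arms.

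**The concern.** Randomizing students balances the students. It does not balance the place where they wait and are measured. Anxiety, heart rate and blood pressure are recorded around a quarter of an hour of sitting in that place, so noise, temperature or nearness to the recording area could plausibly move them. If one classroom always hosts music and the other always hosts quiet, room and arm are the same variable. A difference between arms is then equally a difference between rooms.

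A two-group pilot cannot avoid this. Phase 2 runs more groups and could, but the text carries the pilot's arrangement forward. The resulting bias does not shrink as students are added. The test only becomes more likely to declare it significant.

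**Working it through.** The plan gives no figure on this point except its alpha of 0.05. The check therefore has three parts: what the text implies, how many sessions are available, and an illustration of size.

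**1. Is room aliased with arm?** The music arm is in one reserved room and the control arm in a second. The procedures apply to both phases, with no intended change in methodology. No rotation is described. Followed literally, the indicator for room equals the indicator for arm in every session. A model holding both terms cannot be estimated, and adding sessions does not change that.

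**2. Is there room to rotate in Phase 2?** The slot phrase is ambiguous.

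- 6 students in total per half-hour: 108 / 6 = 18 half-hours.
- 6 students per room, two rooms: 108 / 12 = 9 half-hours.
- 6 slots of up to 10 students each: 108 / 60 = 1.8, so about 2 half-hours.

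Whichever reading applies, groups of at most 10 mean at least 11 groups (108 / 10 = 10.8).

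**3. How large could the effect be?** Assumptions, none taken from the documents:

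- an even 54:54 split of about 108, with everyone taking part;
- independent observations;
- no music effect;
- a room effect d of 0.2 or 0.3 SD;
- where baseline is used, a baseline to follow-up correlation r = 0.5.

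The test is a two-sided two-sample t-test with n = 54 per arm, 106 degrees of freedom and alpha 0.05. The noncentrality is δ = (offset / SD) × √(n/2), with √27 = 5.196. The false-positive rate is the probability that a noncentral t with this δ falls beyond either critical value.

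| Case | Offset left | SD | δ at d = 0.2; 0.3 | False-positive rate |
|---|---|---|---|---|
| No baseline adjustment | d | 1 | 1.039; 1.559 | 17.8%; 33.9% |
| Baseline-adjusted, effect wholly after baseline | d | √(1 − r²) = 0.866 | 1.200; 1.800 | 22.1%; 43.0% |
| Baseline-adjusted, stable offset present at baseline | d(1 − r) = 0.5d | 0.866 | 0.600; 0.900 | 9.1%; 14.5% |
| Change score, stable offset present at baseline | d − d = 0 | √(2(1 − r)) = 1 | 0; 0 | 5%; 5% |

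A change score gives no protection when the effect arises after baseline: the offset is d and the SD is 1, so the first row applies again.

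For comparison, at the pilot's 10 per arm with no baseline adjustment, d = 0.2 gives δ = 0.2 × √5 = 0.447 and a rate of 7.1%. Enlarging the trial without rotating rooms raises the rate from 7.1% to 17.8%.

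**4. What does balanced rotation do?** If each arm has half its students in each room, the room effect adds d/2 to both arm means, and the difference is d/2 − d/2 = 0. Room and arm are then separate variables, and a room term can be fitted.

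**The case against.** The strongest reply has four parts.

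- **Researcher and watches.** A reader might infer that the attending researcher and the watch set also go with the arm. The documents do not support this. They mention a researcher without number and synced watches without allocation. One researcher and one pool of watches serving both rooms fits the text equally well. These are possible confounders only.
- **A fixed room in every session.** A reader might also infer a stated rule that the same physical room serves the same arm throughout. The text says a second reserved classroom, which describes two rooms in use and does not name which is which. That rotation is absent is what the plan leaves unsaid, not something it lays down. This stands as a limit on the claim. Even so, a team following the text has no instruction to swap.
- **Baseline measurement.** The STAI and vital signs are taken before the music, apparently in the same room. An offset that is stable over the visit is partly or wholly removed by using baseline, as the last two rows of the table show. This stands, and it means that 18% and 34% should not be quoted alone. It does not help against a room effect that builds up during the 15 minutes, which is also when music is meant to act.
- **No evidence that the rooms differ.** Both are in the same simulation centre, with the same process and the same ban on devices. Students may also leave, so 54 per arm is an upper figure. This stands too. The percentages illustrate what a given offset would do and are not estimates for this trial.

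**Conclusion.** The concern holds for room. As written, Phase 2 gives each arm its own classroom and describes no rotation, so room is confounded with arm. No later analysis could separate music from a room effect that arises during the wait. For researcher and devices the confounding is only possible, because their assignment is not stated.

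The size depends on assumptions that the documents do not settle. For a room effect of 0.2 to 0.3 SD it runs from no inflation (5%, stable offset on change scores), through about 9% to 14% (stable offset, baseline-adjusted) and 18% to 34% (no adjustment), to 22% to 43% (effect wholly after baseline, adjusted). It would be wrong to read this as showing that the two rooms differ or that the trial's error rate is any one of these figures.

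This is more than a missing detail, because a nearly free design change removes the bias in expectation and nothing done after data collection can replace it. It should be settled before Phase 2 starts. If rotation is already intended, the protocol should say so.

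**What to change.** For Phase 2:

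- Before each session, use the online randomizer already in the plan to choose which of the two reserved classrooms plays music, balanced over sessions. With 9 to 18 half-hours this is easy. If the slot wording means only about two half-hours, one swap is still possible, but it separates room from music less well. The slot wording should be clarified at the same time.
- Record room, researcher and watch set for every session.
- If a researcher or a watch set would otherwise stay with one room, alternate them between arms on the same schedule.
- Include room as a term in the model for anxiety, heart rate and blood pressure.

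**Cost.** An allocation sheet, a short protocol change sent to the IRB (Item 6 already provides for approval of Phase 2 changes before implementation), and working overhead audio in both classrooms. Room rotation itself needs no extra students or rooms. Whether alternating researchers affects staffing cannot be judged, because the documents do not describe staffing.
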